10.1.3 FUTURE USE OF STORED SPECIMENS AND DATA

Data records for the ACCESS trial will be stored at the SDCC for at least 10 years after completion of the study. All data are anonymized, with records indexed by alphanumeric IDs; no names, SSNs, hospital record numbers, phone numbers, addresses or other identifiers will be stored at the SDCC.

10.1.4 SAFETY OVERSIGHT

The independent DSMB will ensure the safety of the subjects by monitoring adverse outcomes throughout the trial and by reviewing outcome data for both efficacy and possible harm. In addition, the Board will review the results of interim analyses. The DSMB will review and approve the protocol before the study can commence. The DSMB will evaluate the rate of adverse events between the treatment and control arms at 6-month intervals. The DSMB will also monitor primary and secondary study outcomes between the two groups. The SDCC will forward DSMB recommendations to study investigators, the Institutional Review Boards, the FDA, and the NIH in accordance with federal regulations 45 CFR Part 46 Subpart A, 21 CFR 312, and the investigational device exemption (IDE) regulations. The DSMB will be given password-protected access to the database of deaths and occurrences of survival to hospital discharge with mRS ≤ 3 and occurrences of severe adverse events attributable to advanced reperfusion strategies. These data will be updated on an expedited basis. Members of the DSMB and/or statistical staff at the SDCC may request a conference call of the group at any time.

10.1.5 CLINICAL MONITORING

The sponsor-investigator will permit direct access for the study monitors and appropriate regulatory authorities to the study data and to the corresponding source data and documents to verify the accuracy of these data.

Independent monitoring of the clinical study for clinical protocol and IDE application compliance will be conducted by University of Minnesota's Clinical and Translational Science Institute (CTSI) clinical trial monitoring service.

The CTSI monitors will confirm that study activities are in compliance with the approved protocol and applicable regulatory authorities (FDA, IRB, local and State regulations).

A Clinical Events Committee (CEC) will include Cardiac Surgery Professor and ECMO surgical director [name] MD PhD, and Associate Professor of Surgery and Critical Care Medicine [name] MD, who is the medical ECMO director at the University of Minnesota and [name] MD (interventional Cardiology). They will review and adjudicate serious and unexpected adverse events independently from the PI and co investigators.

Frequency of monitoring visits will occur:

- After IRB approval
- As soon as possible after the first subject is enrolled
- During the study data collection phase
- After the last subject has completed his/her participation in the study

This monitoring schedule may be revised based on the following considerations:

- Accrual rate
- Protocol deviations or non-compliance with regulatory authorities
- Magnitude of data corrections required
- Study stage (e.g. start-up or follow-up)
- Complexity of the trial
- Request (IRB, Investigator, other etc.)
- DSMB recommendation

Monitoring visits will be performed annually, at a minimum. The sponsor-investigator will permit direct access to the study monitors and appropriate regulatory authorities to the study data and to the corresponding source data and documents to verify the accuracy of these data.

Primary responsibilities of the monitors will include verifying the following:

- Investigator qualifications
- Facilities and equipment
- Storage, dispensing and disposition of investigational products
- Protocol compliance
- Informed consent
- Training and delegation of authority
- Subject eligibility
- Recruitment, screening and enrollment
- Verification of data and data clarification
- Adverse event reporting
- FDA correspondence
- Deviations

10.1.6 QUALITY ASSURANCE AND QUALITY CONTROL

The data management system includes daily off-site backup of all files. Data analyses will be carried out using SAS (version 9.3 or later) or R (version 3.2 or later).

Data quality monitoring will include daily consistency checks to cover issues that cannot be addressed upon data entry. Corresponding query reports will be made available on the internal study website for clinical staff to review and follow-up. Privacy will be maintained by password access to the REDCap system, with timed sessions that close automatically if no activity is detected. All staff with access to clinical records are required to have training in the areas of Good Clinical Practice (GCP), Health Insurance Portability and Accountability Act (HIPAA), responsible conduct of research, and conflict of interest (<https://about.citiprogram.org>). A staff roster will be maintained in a separate REDCap project to track the status and training of all study personnel. Clinical staff who require database access will have individual login credentials, which are made available only as needed during their time on the study.

10.1.6.1 DATA COLLECTION AND MANAGEMENT RESPONSIBILITIES

The investigator-sponsor will maintain records in accordance with Good Clinical Practice guidelines; to include:

- FDA correspondence related to the IDE application and Investigational Plan; including copies of submitted [Form](#) FDA 3500 A, supplemental IDE applications, current investigator lists, progress reports, notice of device recall or disposition, and failure to obtain informed consent reports;
- IRB correspondence (including approval notifications) related to the clinical protocol; including copies of adverse event reports and annual or interim reports;
- Current and past versions of the IRB-approved clinical protocol and corresponding IRB-approved consent form(s)
- Signed Investigator's Agreements and Certifications of Financial Interests of Clinical Investigators;
- Curriculum vitae (investigator-sponsor and clinical protocol sub-investigators);
- Certificates of required training (e.g., human subject protections, Good Clinical Practice, etc.) for investigator-sponsor and listed sub-investigators;
- Normal value(s)/range(s) for medical/laboratory/technical procedures or tests included in the clinical protocol;
- Laboratory certification information;
- Instructions for on-site preparation and handling of the investigational device and/or study treatment or diagnostic product(s), and other study-related materials (i.e., if not addressed in the clinical protocol);
- Decoding procedures for blinded trials;
- Master randomization list;
- Signed informed consent forms;
- Completed Case Report Forms; signed and dated by investigator-sponsor;
- Source Documents or certified copies of Source Documents;
- Monitoring visit reports;
- Copies of investigator-sponsor correspondence to sub-investigators, including notifications of adverse effect information;

- Subject screening and enrollment logs;
- Subject identification code list;
- Investigational drug accountability records, including documentation of device disposal;
- Interim data analysis report(s); and the
- Final clinical study report.

Data in ARREST are entered using the REDCap data entry system and stored in secure files at the Statistical and Data Coordinating Center (SDCC). Patients are identified ONLY by an anonymized alphanumeric patient ID (PID): an example would be mu40238. The SDCC does not receive or store any participant names, SSNs, hospital numbers, or other identifying information. No directly identifiable information regarding participants will appear in any reports, publications, presentations, or other disclosures of clinical study outcomes in the ARREST trial. Access to any participant data stored in SDCC.

The University of Minnesota Data Coordinating Center (SDCC) will provide web-based HTML forms, implemented using REDCap (Research Electronic Data Capture) software, to collect necessary information from the participating study sites. Web entry forms will have dynamic features such as immediate checks on data and relationships within a form and between forms. Details and clarification about data items will be provided using pop-up windows and links to appropriate sections of the on-line version of the Manual of Operations. Data encryption and authentication methods will be used. The SDCC will build additional features into the web entry forms including: forms transmission history, access to past forms, tracking of data corrections, and the capability to save and re-load incomplete forms. The central data management system will be ORACLE, which has been used by studies at the Coordinating Centers for Biometric Research (CCBR) for over 30 years. CCBR staff have developed methods for importing data from REDCap into ORACLE, with capability for sophisticated, comprehensive edits using utilities developed at the CCBR. The ORACLE Database Management System (DBMS) includes daily off-site backup of all files. Access to the database will be password-protected and permissions granted only to ARREST data coordinating center staff. Data analyses will be carried out using SAS (version 9.3 or later) or R (version 3.2 or later).

All data files are backed up to a remote location on a daily basis, and can be restored by designated data management personnel in case of system failures or power outages. Access to our system by unauthorized entities is closely monitored. The REDCap system automatically includes a data dictionary and complete specifications with regard to data type (e.g., numeric, character, dates, ICD-10 codes, other).

The investigator-sponsor will retain the specified records and reports for up to 2 years after the marketing application is approved for the investigational device; or, if a marketing application is not submitted or approved for the investigational drug, until 2 years after investigations under the IDE have been discontinued and the FDA so notified.

Subject names or other directly identifiable information will not appear on any reports, publications, or other disclosures of clinical study outcomes.

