5.2 EXCLUSION CRITERIA

- Age < 18 years old or > 75 years old;
- Non-shockable initial OHCA rhythm (pulseless electrical activity [PEA] or asystole);
- Valid do-not-attempt-resuscitation orders (DNAR);
- Blunt, penetrating, or burn-related injury, drowning, electrocution or known overdose;
- Known prisoners;
- Known pregnancy;
- Nursing home residents;
- Unavailability of the cardiac catheterization laboratory.
- Severe concomitant illness that drastically shortens life expectancy or increases risk of the procedure;
- Absolute contraindications to emergent coronary angiography
 - Known anaphylactic reaction to angiographic contrast media
 - Active gastrointestinal or internal bleeding

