Early ECMO facilitated Resuscitation Arm. Following the standard EMS call to a central telephone number, if the research team determines the possible study subject would be randomized to the Early ECMO Facilitated Resuscitation Arm if entered in the study, they will begin mobilization of the CCL/ECMO team. EMS providers transport the patient to the University of Minnesota Medical Center, Fairview Hospital using the LUCAS device for CPR. Resuscitation interventions, including intravenous epinephrine, antiarrhythmics, defibrillation, and other appropriate treatments, occur prior to and during transport per EMS policy and procedure. Immediately following hospital arrival, the research team will evaluate the ARREST Trial inclusion and exclusion criteria and, if eligible, randomize and enter the patient in the study, directing the patient's hospital-based disposition. If the CCL/ECMO team is not in-house and has not yet arrived, resuscitation continues in the ED resuscitation area until arrival of the CCL/ECMO team. In this circumstance, given that average EMS transport times are 15 ± 5 minutes, it is expected that resuscitation will continue following arrival in the ED for about 10-15 minutes until CCL

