6.3 MEASURES TO MINIMIZE BIAS: RANDOMIZATION AND BLINDING

Patients eligible for this study will be VT/VF OHCA patients refractory to standard treatment as defined by the ARREST Trial inclusion and exclusion criteria. Initially patients will be randomly allocated in a 1:1 ratio immediately following hospital arrival. As noted in the Statistical Considerations section, this trial has a Bayesian Adaptive Design, which means that the treatment allocation ratio may be changed later to reduce the probability of assignment to an inferior treatment arm. See Section 9 below. The study has been designed to minimize treatment bias as far as possible. EMS providers will be blinded to the study. University of Minnesota Refractory VF/VT Protocol patients are placed on LUCAS and transferred to the University of Minnesota with ongoing mechanical CPR per standard of care. All out-of-hospital care, including CPR, ACLS, and resuscitation efforts, will be implemented using ACLS guidelines and automated CPR (LUCAS™2) and treatment will be unchanged. Patients will be randomized and entered in the study by research personnel only after hospital arrival and assessment of ARREST Trial inclusion and exclusion criteria. Emergency department personnel will be aware of group assignment. However, ED treatment of all patients follows protocol and standard of care. CCL personnel also will be aware of group assignment, but treatment is similarly protocolized. Post-CCL care in the CICU will be blinded to group assignment. Patients in both groups could have received identical treatment. Patients from both groups will be treated with the same established CICU post arrest protocol by the same critical care team. The PIs will not be involved in any end-of-life decision making. The **Figure** below shows the phases of care in which providers are blinded to group allocation (in light blue).

Thus, we expect patients in both groups to similarly reflect the gender, ethnic diversity, severity or duration of cardiac arrest, and receive the same therapy except early ECMO facilitated resuscitation versus standard ACLS resuscitation.

[figure not shown]

Figure: Patient flow chart showing blinding.

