Let Y_i indicate whether the i^{th} participant survives to hospital discharge which we assume follows a Bernoulli distribution with probability of response p_a when this participant is assigned to group $a = E$ or C . We specify independent Uniform(0,1) \equiv Beta(1,1) prior distributions for p_E and p_C . Let N_a denote the number of participants assigned to group a and X_a the number of responses. It follows that the posterior distribution for p_a is Beta(X_a+1 , $N_a - X_a + 1$) and

$$\text{Prob}(p_E > p_C | \text{Data}) = \int_0^1 [1 - F(y | X_E + 1, N_E - X_E + 1)] f(y | X_C + 1, N_C - X_C + 1) dy$$

where $F(y | a, b)$ and $f(y | a, b)$ respectively denote the Beta(a,b) cumulative distribution and probability density functions. Note that $\text{Prob}(p_E < p_C | \text{Data}) = 1 - \text{Prob}(p_E > p_C | \text{Data})$. We calculate $\text{Prob}(p_E > p_C | \text{Data})$ in R v3.5.1 using adaptive quadrature via the `integrate()` function.

Group Sequential Adaptive Design

We will calculate $\text{Prob}(p_E > p_C | \text{Data})$ each time we ascertain an evaluable outcome on 30 participants, and stop the trial for superiority when $\text{Prob}(p_E > p_C | \text{Data}) \geq 0.986$, or for inferiority when $\text{Prob}(p_E < p_C | \text{Data}) \geq 0.986$. If the trial does not stop, the next group of enrollees will be randomized to ECMO with probability equal to the current value of $\text{Prob}(p_E > p_C | \text{Data})$ subject to the restriction that the randomization ratio may not exceed 3:1 in either direction. The initial cohort of patients will be randomized 1:1. Upon ascertaining evaluable outcomes on 150 participants, if neither posterior probability threshold for superiority or inferiority is exceeded the trial will be stopped with a failure to reject the null. This maximum sample size was chosen to provide 90% power for the targeted alternative scenario of with $p_E = 0.37$ versus $p_C = 0.12$ as evidenced by the computer simulation study reported below.

Operating Characteristics

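### Section 10.1.6.1 files the randomisation list and interim reports with the investigator-sponsor with no time limit or firewall, so allocation concealment is not protected as written

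*Combined protocol and SAP*

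**What the plan says.** Section 10.1.6.1 opens its list of files with "The investigator-sponsor will maintain records in accordance with Good Clinical Practice guidelines; to include". Among the entries are the "Master randomization list" and the reports of the interim analyses. Neither entry carries a time of access, a restriction or a separate custodian. No other section describes how the sequence is generated, concealed or released.

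The setting in which those records sit:

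- **Who enrols.** Section 6.3: "Patients will be randomized and entered in the study by research personnel only after hospital arrival" and after the entry criteria have been assessed. Section 6.1.1 says the same of the research team.
- **What is judged.** Section 5.2 includes "Severe concomitant illness that drastically shortens life expectancy or increases risk of the procedure", which calls for judgement at the bedside.
- **Who knows the arm.** Section 4.1 calls the trial partially blinded. ED and catheterisation-laboratory (CCL) staff know the assignment; intensive-care staff and outcome assessors are meant not to.
- **Exclusion after randomisation.** Sections 5.3 and 9.3 allow it and remove those patients from the ITT population.
- **Advance knowledge.** In the early-ECMO paragraph of section 6.1.1, after the EMS call, CCL/ECMO mobilisation begins "if the research team determines the possible study subject would be randomized to the Early ECMO Facilitated Resuscitation Arm if entered in the study". Section 5.4 and the screening paragraph of section 6.1.1 instead have that team activated by the call whatever the arm.
- **Allocation rule.** Section 9.1: after each look, "the next group of enrollees will be randomized to ECMO with probability equal to the current value of" the posterior probability that ECMO is better, limited to 3:1 either way.

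**The concern.** Random allocation protects the comparison only if whoever decides that a patient is eligible cannot foresee the arm. Here sponsor and investigator are one party at one centre, so the usual distance between list-holder and recruiter is missing unless the plan creates it. It does not.

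If the next arm is foreseeable, a judgement about concomitant illness can lean one way before ECMO and the other way before standard care, without any intent to mislead. Exclusion after randomisation gives a second opportunity, made by people who may know the arm. The arms are small and survival is low, so a modest imbalance in prognosis reaches the primary endpoint directly. The type I error claim in section 9.1 assumes none.

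The interim reports raise a different matter. They show the emerging efficacy result to the party that enrols and treats.

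**Working it through.** **1. Plan's own figures.** Inputs from section 9.1: Beta(1,1) priors, looks at 30, 60, 90, 120 and 150, stop at posterior 0.986 in either direction, next cohort's ECMO probability limited to 0.25–0.75, null 0.12 in both arms, alternative 0.37 v 0.12. With 10,000 simulated trials per scenario and simple 1:1 allocation in cohort 1:

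| Scenario | Rejection, plan | Rejection, re-run | Mean N, plan | Mean N, re-run |
|---|---|---|---|---|
| Null | 0.048 | 0.049 | 148.5 | 146.9 |
| Alternative | 0.905 | 0.904 | 81.6 | 82.1 |

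The rejection rates agree within simulation error (about 0.002 under the null). The design itself is not in question.

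**2. What each record reveals.** A list can run ahead only to the end of the current 30-patient cohort, because the ratio then changes. Within that cohort it gives every next arm. The allocation probability alone gives a correct guess 50% of the time in cohort 1, 67–68% on average in later cohorts under the null and 72–75% under the alternative. It is never above 75%, and is about 64–65% over the whole trial.

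**3. Illustration: the list is known.** Prognostic spread comes from the historical cohort in section 2.3.2. Patients with CPR of 40 minutes or more number 99+69+29+11+3+7 = 218 of 636, or 34.3%, with no survivors. Let *f* be the fraction of zero-survival patients passed over when ECMO is next, and the same fraction of the others passed over when standard care is next. With true survival of 0.12 in both arms:

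- pE = 0.12 / (1 − 0.343*f*)
- pC = 0.12(1 − *f*) / (0.657(1 − *f*) + 0.343)

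At *f* = 0.3: pE = 0.12/0.897 = 0.134 and pC = 0.084/0.803 = 0.105. Running each pair through the design in step 1:

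| *f* | pE | pC | False superiority claims | Total false positives |
|---|---|---|---|---|
| 0 | 0.120 | 0.120 | 0.026 | 0.049 |
| 0.1 | 0.124 | 0.116 | 0.035 | 0.053 |
| 0.3 | 0.134 | 0.105 | 0.063 | 0.071 |
| 0.5 | 0.145 | 0.089 | 0.124 | 0.127 |

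**4. Only the probability is known.** The probability is constant within a cohort, so the guess is the same for all 30 patients. Any selection then falls on both arms of that cohort alike, leaving only slight confounding between cohorts. With selection on the likelier arm from cohort 2 onward (20,000 trials), the total was 0.048, 0.048 and 0.049 at *f* = 0.1, 0.3 and 0.5, against 0.051 with none. False superiority claims were 0.026, 0.028 and 0.032, against 0.027. Across all re-runs of this route the total stayed between 0.047 and 0.054.

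**The case against.** **It is a filing list.** Section 10.1.6.1 also names drug accountability records, in a device trial, and the final study report, which cannot exist during enrolment. It says what is kept, not who looks or when. This stands. A reader might infer that upcoming assignments are in fact open to the enrolling team; the section does not say so. But it is the only text on custody of these records, and section 6.1.1 does describe the team determining the arm in advance.

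**Other text points the other way.** Section 10.1.6.1 limits the central database to coordinating-centre staff, and sections 9.4.6 and 10.1.4 send interim results to the DSMB. Section 5.3 says later exclusions will rest on objective factors unrelated to the arm. The database rule does not mention the list, the DSMB text does not bar the investigators, and section 5.3 names no one unaware of the arm to make the decision. The manual of procedures may hold more, but it is not among the documents.

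**The interim report is not as revealing as the list.** This stands. A reader might carry the 75% guess over to the false-positive figures; step 4 shows that it does not carry over.

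**The illustration fits loosely.** This also stands. CPR duration is not an eligibility criterion, and its final value is unknown on arrival. The historical mix is not the local one: 19+29+31+25+16+7 = 127 of 143 local ECPR patients (89%) had 40 minutes or more, and about 20% survived at 60–89 minutes. The judgement criterion in section 5.2 has no stated prognostic spread.

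**Withholding interim reports hides little.** Partly right. One site can count its own survivors by arm and apply the published rule.

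**Conclusion.** The point holds as a gap in protection. The plan assigns both records to the investigator-sponsor without limit, states no concealment procedure, and in section 6.1.1 describes knowledge of the arm before eligibility is settled. Followed as written, it can defeat concealment. It does not show that anyone consulted the list or selected patients, and the trial should be called partially blinded, not open.

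The size is illustrative. It rests on perfect knowledge of every next assignment, an assumed steering fraction and a borrowed 34% zero-survival group. On those terms 10% steering hardly changes the total, 30% adds about 0.02 (0.071 − 0.049), and 50% more than doubles it (0.127/0.049 = 2.6). None of this applies to the interim reports, where the issue is exposure to the emerging result. The point merits a change because the remedy is cheap and protects the error rate that section 9.1 claims.

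**What to change.** In section 10.1.6.1, state that until primary-outcome lock:

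- SDCC staff outside the enrolling team hold the randomisation list and the current allocation ratio, and release each assignment only after eligibility has been entered;
- interim analysis reports go only to the DSMB;
- both sets of records pass to the investigator-sponsor's file after lock.

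Reconcile the early-ECMO paragraph of section 6.1.1 with its screening paragraph and with sections 5.4 and 6.3, so that the plan gives one account of when the arm becomes known and what activates the CCL/ECMO team.

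The cost is protocol wording and a release step; the SDCC and its REDCap system already exist. The downside is that the investigator-sponsor's file is incomplete until lock. Restricting the reports limits sight of the emerging result but cannot remove it at a single site.
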